### Renal laboratory parameters

All calculations for the grading of renal function will be based on the originally measured laboratory values and the ULNs given by the laboratory, not on normalised values with BI standard reference ranges.

The creatinine clearance (Ccr) and glomerular filtration rate (GFR) will be estimated according to the two formulas:

- Cockcroft-Gault formula [mL/min]:  

$$e\text{Ccr} = (140 - \text{age}) \times (\text{weight [kg]} \times (0.85 \text{ if female}) / (72 \times \text{serum creatinine [mg/dL]})$$
- Japanese equation [mL/min/1.73m^2]:  $e\text{GFR} (\text{mL/min/1.73m}^2) = 194 \times [\text{serum creatinine (mg/dL)}]^{-1.094} \times [\text{age}]^{-0.287} \times [0.739 \text{ if patient is female}]$

Age will be considered as a discrete variable for the above calculations, and the age will be from the same visit as the other variables. The weight used in the calculations will be that from the same visit, if available. If a value is not available, an interpolated value from the previous and subsequent visits will be used. If no subsequent value is available an LOCF approach will be used. Baseline values will not be interpolated.

For the analysis of eGFR and for the covariates in the statistical modelling, the values calculated from the above formula using the serum creatinine values from the central laboratory will be used, not the eGFR values provided by the central laboratory. For the assignment of PVs based on renal function, the central laboratory values will be used.

Staging of the eGFR will be categorized according to the following staging:

Table 7.8.2: 1 Japanese equation eGFR staging

Stage	eGFR [mL/min/1.73m  ]	Description
1	≥90	Normal renal function
2	60 to <90	Mild renal impairment
3	30 to <60	Moderate renal impairment
4	<30	Severe to end-stage renal impairment

Staging of the eCcr will be categorized according to the following staging:

Table 7.8.2: 2 Cockcroft-Gault eCcr staging

Stage	eGFR [mL/min]	Description
1	≥90	Normal renal function
2	60 to <90	Mild renal impairment
3	30 to <60	Moderate renal impairment
4	<30	Severe renal impairment and beyond (e.g., End-stage renal disease)

Descriptive statistics will be created for creatinine and eGFR values over time. Descriptive statistics for eCcr will be presented in the CTR, Appendix 16.1.9.2. These data will be used to create plots of the parameters over time. Subgroups tables of these descriptive statistics at Week 52 will also be presented for age subgroups.

A summary will also be created representing the number of patients with creatinine on treatment  $\geq 2$  x baseline and greater than the upper limit of normal.

A shift table from baseline to last value on treatment for eGFR (Japanese equation) will be provided in the CTR, Section 15 and eCcr (Cockcroft-Gault) will be provided in the CTR, Appendix 16.1.9.2.

In addition, urine albumin and urine albumin / creatinine ratio will be summarised in the CTR. Urine creatinine does not have a reference range and it is determined to calculate the albumin / creatinine ratio. Only the albumin / creatinine ratio will be analysed as for urine creatinine, no normalised values can be derived. In cases where urine albumin values are reported to be below the quantification limits (e.g. <3 mg/L), the albumin / creatinine ratio is determined as missing and will not be replaced by estimated values.

Four summaries will be presented for the descriptive statistics of urine albumin/creatinine ratio by baseline value (normal ( $<30$ mg/g), microalbuminuria ( $30-300$  mg/g) and macroalbuminuria ( $\geq 300$  mg/g)), descriptive statistics of urine albumin by baseline value ( $<20$ mg/L,  $20-200$ mg/L and  $\geq 200$ mg/L) and frequency of transitions from baseline based on the before mentioned categories.

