Proprietary confidential information © 2017 Boehringer Ingelheim International GmbH or one or more of its affiliated companies

Safety laboratory parameters – whole blood, serum or plasma

(continued)

Bone Marker (only at selected visits)

iPTH

Table 5.3.3: 1

- 25OH Vitamin D
- NTx in Urine

FFA and Ketone bodies (only at selected visits)

- Total ketone body
- Acetoacetic acid
- 3-hydroxybutyric acid
- Free fatty acid (FFA)

Table 5.3.3: 2 Safety laboratory parameters – urine

Urinalysis

Semi quantitative (dipstick)

- Nitrite*
- Protein
- Ketone
- Urine pH
- Leukocyte esterase (for WBC)*

Quantitative

- Albumin
- Creatinine

Microscopic analysis

Will be performed as reflex test if any of the semi quantitative tests/dispsticks are abnormal:

- Urine RBC/Erythrocyte
- Urine WBC/Leukocytes
- Urine sediment microscopic examination
- Urine culture (including antibiogram test):
 - reflex test triggered by positive leukocyte esterase (for WBC) and/or nitrite in the semi-quantitative test/dipstick

Albumin/creatinine ratio in spot urine will be calculated at the central lab.

Glomerular filtration rate

The eGFR will be derived from serum creatinine values for Japanese equation: eGFR (mL/min/1.73m²) = 194 x [Screatinine (mg/dL)]^{-1.094} x [age]^{-0.287} x [0.739 if patient is female]

Renal function impairment will be classified in the following way:

- No renal function impairment: eGFR >90 mL/min/1.73m²;
- Mild renal function impairment: eGFR 60 to <90 mL/min/1.73m²;
- Moderate renal function impairment: eGFR 30 to <60 mL/min/1.73m²;
- Severe renal function impairment: eGFR <30 mL/min/1.73m².

^{*} Nitrite and leukocyte esterase (for WBC) will be determined both locally on site (not recorded in eCRF) and via central lab. A positive result at site triggers the sampling of mid-stream urine for urine culture.

These classes of renal impairment will be the basis for stratification of subgroup analysis.

Pregnancy testing

Pregnancy testing (urine) will be performed in female patients of child bearing potential only according to the time points indicated in the flow chart.

Criteria for hypoglycaemic events

Every episode of glucose concentrations ≤70 mg/dL (3.9 mmol/L) should be documented in the eCRF with the respective time and date of occurrence. Any hypoglycaemia with glucose concentrations <54 mg/dL (<3.0 mmol/L) and all symptomatic and severe hypoglycaemias should be documented as an AE "hypoglycaemic event".

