### **Safety and other variables**

Missing safety data will not be replaced, but an analysis of the changes from baseline to the last available value under treatment and the minimum and maximum post baseline will be determined for quantitative safety laboratory variables.

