#### Values below/above limits of quantifications

For biomarkers (insulin, glucagon) we will replace the values which are below the lower limit of quantification (LLQ) with 2/3 times LLQ. This is approximately the median of the expected “true” value if the biomarker follows a normal distribution. We will replace the values which are above the upper limit of quantification (ULQ) with 3/2 times ULQ. With this approach even a change of the method with different limit of quantifications can be handled within a trial. The number of below the LLQ will be included in the biomarker table.

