## **7. PLANNED ANALYSIS**

For End-of-Text tables, the set of summary statistics is: N (number of patients with nonmissing values) / Mean / SD / Min / Q1 / Median / Q3 / Max.

Tabulations of frequencies for categorical data will include all possible categories and will display the number of observations in a category as well as the percentage [%] relative to the respective treatment group. Percentages will be rounded to one decimal place. The category missing will be displayed if and only if there are actually missing values. Percentages will be based on all patients in the respective patient set whether they have non-missing values or not.

Disposition of the patient population participating in the trial will be analysed by treatment groups on the SCR and presented in the CTR as a frequency-distribution. Reason for not randomising screened patients will be tabulated on the SCR.

The frequency of patients in different analysis sets will also be analysed for each treatment group.

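### Setting the urine albumin/creatinine ratio to missing when albumin is below the quantification limit raises the displayed quartiles and files known-normal results as missing

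*SAP*

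**What the plan says.** SAP 7.8.2, Renal laboratory parameters, covers samples with urine albumin reported below the quantification limit and gives <3 mg/L as an example. For these, "the albumin / creatinine ratio is determined as missing and will not be replaced by estimated values". The same subsection then summarises the ratio by baseline class (normal <30 mg/g, microalbuminuria, macroalbuminuria) and tabulates transitions from baseline between these classes.

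SAP 7 computes the summary statistics, including median and quartiles, on patients with non-missing values. For frequency tables, "The category missing will be displayed if and only if there are actually missing values", and "Percentages will be based on all patients in the respective patient set whether they have non-missing values or not".

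SAP 6.6 sets the general policy: "Missing safety data will not be replaced". It also holds the SAP's one other below-limit rule: "For biomarkers (insulin, glucagon) we will replace the values which are below the lower limit of quantification (LLQ) with 2/3 times LLQ". There the number below the limit is shown in the table. Urine albumin gets neither the substitution nor the count.

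Protocol 5.3.3 lists urine albumin and urine creatinine as quantitative parameters and adds: "Albumin/creatinine ratio in spot urine will be calculated at the central lab".

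**The concern.** A below-limit albumin is a reported result that bounds the ratio from above by limit/creatinine. The rule removes a value because it is low, so it always takes from the bottom of the distribution, and every displayed quartile rises.

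The baseline-normal class is hit hardest, because nearly all deleted baseline values belong there. In the micro- and macroalbuminuria classes the effect arises only on treatment: a patient whose albumin falls below the limit is recorded as missing instead of moving to normal. Where a table uses the last available on-treatment value, an earlier and probably higher ratio may stand in for a final below-limit one.

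In the frequency tables the normal and normal-to-normal cells look too small. The difference sits in a missing row that does not separate results too low to quantify from samples never taken. With 32 patients per arm, a few such patients visibly change a renal safety table.

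**Working it through.** **Patients per arm.** Protocol 7.7 needs 50 completers in total with about 20% dropout: 50/(1 − 0.20) = 62.5, rounded up to 63, or 32 per arm with equal arms. This reproduces the protocol's figure. Neither document states an expected share of albumin values below the limit.

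**When a deleted sample is provably normal.** The ratio is below limit/creatinine. Setting this equal to 30 mg/g:
- limit 3 mg/L: 3/30 = 0.1 g/L = 10 mg/dL urine creatinine;
- limit 5 mg/L: 5/30 = 0.167 g/L = 16.7 mg/dL.

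At a limit of 3 mg/L, the upper bounds at creatinine 20, 50 and 100 mg/dL are 15, 6 and 3 mg/g. Creatinine is measured, so the check can be made sample by sample.

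**Direction.** If the lowest fraction f is removed, the displayed p-quantile is the true quantile at f + (1 − f)p. For f = 20% the displayed median is the true 0.20 + 0.80 × 0.50 = 60th percentile. For a lognormal with log-SD 1.0 that is exp(0.253) = 1.29 times the true median. At f = 5%, 10% and 30% the factor is 1.06, 1.13 and 1.47.

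**Size, under stated assumptions.** None of these inputs is in the documents except the example limit:
- limit 3 mg/L;
- log ratio = patient effect (SD 1.1) + visit error (SD 0.5), with no true change;
- urine creatinine lognormal, median 1 g/L, log-SD 0.5;
- median ratio 5, 8, 12 or 20 mg/g.

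Log albumin then has SD √(1.1² + 0.5² + 0.5²) = 1.308. At median 8 the share below the limit is Φ((ln 3 − ln 8)/1.308) = Φ(−0.75) = 23%, or about 7 of 32 patients per arm. At medians 5, 12 and 20 it is 35%, 14% and 7% (about 11, 5 and 2 of 32). Simulation with 400,000 patients per scenario gives the table below; Monte Carlo error can move the last digit.

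| Assumed median ratio (mg/g) | Below limit | Overall median: true / displayed / with 2/3 limit | Baseline-normal median: true / displayed | Normal, % of all: true / displayed | Normal-to-normal, %: true / displayed |
|---|---|---|---|---|---|
| 5 | 35% | 5.0 / 8.6 / 5.1 | 4.5 / 7.7 | 93 / 58 | 90 / 44 |
| 8 | 23% | 8.0 / 11.3 / 8.0 | 6.5 / 9.2 | 86 / 64 | 81 / 49 |
| 12 | 14% | 12.0 / 15.0 / 12.0 | 8.5 / 10.6 | 78 / 63 | 71 / 49 |
| 20 | 7% | 20.0 / 22.4 / 20.0 | 11.2 / 12.7 | 63 / 56 | 54 / 43 |

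At median 8 the quartiles are 3.6 to 18.1 in truth, 6.2 to 22.7 as displayed, and 3.8 to 18.1 with 2/3 of the limit. Essentially all deleted samples are provably normal, and classifying by the bound restores the normal-to-normal cell fully.

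**Sensitivity.** With a limit of 3 to 5 mg/L and median creatinine of 0.6 to 1.4 g/L, 4% to 65% of samples fall below the limit, and at least 98.5% of those are provably normal. A second set of 24 scenarios kept the 3 mg/L limit, with log-SD 0.9 or 1.2 and correlation of ratio with creatinine from 0 to −0.5. All three quartiles were displayed too high in every one. The share below the limit ran from 0.8% (median 20.0 displayed as 20.2) to 35.2%.

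**What is not distorted.** With all patients as denominator, the abnormal percentage at median 8 is 13.7% in truth and 13.7% as displayed, and normal-to-abnormal is 5.0% in both. Overall mean log change is 0.00 when nothing truly changes.

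**The case against.** The rule is openly stated, follows the no-replacement policy for safety data (Protocol 7.5, SAP 6.6) and treats both arms alike. The insulin and glucagon rule is confined to those biomarkers, so the SAP does not contradict itself. The laboratory computes the ratio and may deliver none when albumin is reported only as below the limit. The missing row and the all-patient denominator keep abnormal percentages honest. The mg/L albumin summary may still show these patients, and the shifted class medians remain far below 30 mg/g. The size is wholly assumed, and the most striking figures come from the lowest assumed median.

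Much of this stands, and it keeps the point minor. It does not repair the quartiles or the normal cells. A result reported as below the limit is not absent data, and stating the rule in advance does not undo a deletion that depends on the value. The SAP does not say how below-limit albumin enters the mg/L tables, and the laboratory guideline it cites is not available here.

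Substitution also has a fair objection. Protocol 4.2.2.2 notes a diuretic action of the drug class, so on-treatment urine may be more dilute, and 2/3 of the limit over a lower creatinine creates an artificial rise. If median creatinine fell from 1.0 to 0.75 g/L with no true change, overall mean log change would be +0.078 with substitution against +0.036 with deletion at median 5, and +0.046 against +0.027 at median 8. In the planned baseline-normal display at median 8, substitution is nearer the truth: 0.105 against 0.123, true value 0.053. Classification by the bound and the below-limit count avoid this problem.

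**Conclusion.** The concern holds, as a minor point. The direction follows from the rule whenever any sample is below the limit: displayed ratio quartiles are too high, and results that provably meet the SAP's own normal definition are tabulated as missing. Confidence is high on direction only. The size depends on the unknown albuminuria and urine creatinine distributions and on the actual assay limit, and it runs from negligible when few samples fall below the limit to large when a third or more do. Abnormal percentages, the primary endpoint and the HbA1c analysis are not affected.

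**What to change.** Replace the rule in SAP 7.8.2 with three statements:

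1. When urine albumin is below the limit, compute limit/urine creatinine. If this is under 30 mg/g, class the sample as normal in the baseline-class and transition tables; otherwise leave it unclassified. This uses the observed inequality and estimates nothing.
2. For quantitative ratio summaries, set albumin to 2/3 of the limit, as SAP 6.6 does for insulin and glucagon, and lead with median and quartiles.
3. Show the number below the limit by visit and arm, separately from samples not taken.

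The cost is a few sentences and one ratio derived by the sponsor. The SAP already takes this route for eGFR, where "the values calculated from the above formula using the serum creatinine values from the central laboratory will be used, not the eGFR values" supplied by the laboratory. Item 2 needs a stated exception to the no-replacement policy.

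Item 2 also has limits. Mean change becomes approximate, and the more so if urine is more dilute on treatment. With fewer than 25% below the limit, the median and upper quartile hardly depend on the substituted value, and the lower quartile moved by at most about 0.3 mg/g. With many below the limit the correction is partial: at 50%, a true median of 5.0 shows as 5.9 with substitution, against 11.2 under the current rule.

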### Serum lipid parameters/free fatty acid (FFA)

Lipid parameters (Total cholesterol, HDL, LDL, LDL/HDL ratio, Non-HDL, and Triglycerides) and FFA will be analysed using descriptive statistics and MMRM modelling. Descriptive statistics will be shown over time for the TS (LOCF-IR and OC-IR) including change from baseline and percent change from baseline. For each lipid parameter, separate MMRM models will be fitted on the TS (OC-IR) for both change from baseline and percentage change from baseline. The MMRM models will include “baseline lipid” and “baseline HbA1c” as continuous covariates and “treatment”, “baseline renal function”, “visit” and “treatment-by-visit” interaction as fixed effects.

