- 13. For female patients (local urine pregnancy test in women of child bearing potential)
- 14. Fasting blood samples for central lab testing except for urine dipstick, which is to be done locally; upon positive result at site for leukocyte esterase (for white blood cells [WBC]) or nitrites, a midstream urine sample for urine culture (for central lab analysis) should be taken.
- 15. Self Monitoring Blood Glucose (SMBG) device to be provided at Visit 2 for one OAD, Visit 4 for liraglutide plus one OAD, and Visit 6 for liraglutide alone. Instruction on how the device should be used and the frequency of the measurements should be done when SMBG is provided. Additional instructions and training may be done on other visits as per investigator's discretion and considering patient compliance with protocol-defined measurement and clinical status of the patient.
- 16. Throughout the whole trial participation, SMBG testing is recommended to be done daily prior to breakfast but should be performed at least weekly prior to breakfast and at any time when the patient is symptomatic, i.e., experiences signs/symptoms of hyper- or hypoglycaemia.
- 17. At all the visits, the respective medication number has to be allocated to the patient via IRT.
- 18. For the screening Visit 1, laboratory only includes liver transaminases (AST and ALT), alkaline phosphatase (ALP), serum creatinine, TSH and urinalysis in addition to HbA1c and FPG.
- 19. HbA1c at Visit 6 is to be skipped if patients are on liraglutide alone.
- 20. In case of early discontinuation from double-blind treatment, Visit 15/EOT visit has to be performed within 7 days of the last dose of the study drugs.

- 21. For patients who completed the trial without any persisting adverse event at Visit 15/EOT, a Visit 16 (Follow-up visit) can be performed as a phone visit (only information on SMBG log, adverse events, and concomitant therapies are to be obtained). For patients who completed the trial with persisting adverse event(s) at Visit 15/EOT and patients who prematurely discontinued the 52-week treatment, a Visit 15/EOT and a Visit 16 (as the follow up-visit, physical examination, vital signs, and safety lab and FPG measurement should be performed additionally) should be performed after 7 days of the Visit15/EOT (with +7 days allowance) as clinic visits.
- 22. Only blood sampling for haematology and urine dipstick test will be performed.
- 23. Blood sample can be taken at any time in non-fasted state.

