7.5 HANDLING OF MISSING DATA

As defined for the MMRM, missing data are handled implicitly by the statistical model, rather than by using any imputation (see Section 7.3.2). In case of ANCOVA analyses, missing data will be imputed using the LOCF approach. If no value after first intake of trial medication is available, the baseline value will be used for HbA1c. Further details will be provided in the TSAP.

With respect to safety evaluations, it is not planned to impute missing values.

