### Full analysis set

[figure not shown]
The full analysis set (FAS) will consist of all patients in TS who were treated with at least one dose of the randomised study drug and had a baseline HbA1c assessment. The assignment of patients to treatment groups will be based on the randomised study drug at time of randomisation.

Table 6.3: 1 Patient sets analysed

Class of endpoint	SCR	TS	FAS
Secondary efficacy endpoints			OC, OC-IR, LOCF
Other continuous efficacy endpoints			OC, LOCF
Other binary efficacy endpoints			NCF
Primary safety endpoints		OR	
Other safety endpoints			OR, OC-IR, LOCF-IR
Disposition	OR		
Demographic			OR
Baseline endpoints			OC

OR: Original results, LOCF-IR: Last observation carried forward including values after rescue, OC-IR: Observed case including values after rescue, NCF: Non-completers considered failure

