### **Last observation carried forward (LOCF)**

For quantitative endpoints, missing values will be replaced by the last observed measurement on treatment. If the patient has no on-treatment value, baseline value will be carried forward. This method tends to result in more conservative estimates than an OC-analysis. The values measured after taking rescue medication during the treatment period will be set to missing, and these missing values will be imputed by LOCF approach.

The last observation on-treatment need not necessarily to be a value selected as a visit value if multiple measurements are performed within a time window for a visit. In this case the last on-treatment value within time window will be carried forward, while the visit value can be the value that is observed closest to the planned visit date or the first value observed in the time window. See [Section 6.7](#).

Missing values within a course of measurements on treatment will be interpolated based on the last observed value before the missing visit and the first observed value after the missing visit. This is independent from the selection of a value as the picked visit value to be used in the descriptive analysis by visit.

Let:

$D_0$  = date of a visit with a missing endpoint value;

$D_1$  = date of the next-visit (with end-point value non-missing) after the visit with a missing endpoint;

$D_{-1}$  = date of the previous-visit (with end-point value non-missing) before the visit with a missing endpoint;

$E_i$  = endpoint values for visits  $D_{-1}$ ,  $D_0$ ,  $D_1$  for  $i=-1, 0$  and  $1$ )

Then the missing endpoint value can be interpolated as:

$$E_0 = E_{-1} + ((E_1 - E_{-1}) \times (D_0 - D_{-1}) / (D_1 - D_{-1})).$$

For lipid parameters, it is planned to analyse by using LOCF- technique but including the original observed values after taking rescue medication. That called LOCF including values on rescue medication (LOCF-IR).

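### The SAP plans LOCF-IR tables for lipids and FFA against the protocol's no-imputation rule for safety data, without declaring it; for lipids this could fill three unsampled visits with unmeasured values

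*SAP*

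**What the plan says.** **The rule.** Protocol 7.5: "With respect to safety evaluations, it is not planned to impute missing values". It makes no exception for lipids. The safety paragraph of SAP 6.6 agrees in its opening words: "Missing safety data will not be replaced". SAP 4 reports no departure from the protocol's analysis.

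**The status of the parameters.** Protocol Table 5.3.3: 1 lists total, HDL and LDL cholesterol and triglycerides under clinical chemistry, and FFA in its own block, all as safety laboratory parameters. The SAP analyses them in 7.8.2, within the safety analysis on the treated set.

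**The plan for lipids.** SAP 7.8.2: "Descriptive statistics will be shown over time for the TS (LOCF-IR and OC-IR". The LOCF paragraph of SAP 6.6: "For lipid parameters, it is planned to analyse by using LOCF- technique but including the original observed values after taking rescue medication". SAP Table 6.3: 1 lists "OR, OC-IR, LOCF-IR" for other safety endpoints. The lipid MMRM in 7.8.2 uses OC-IR only.

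**What LOCF does.** Besides carrying the last on-treatment value forward (or baseline if there is none), SAP 6.6 fills gaps between observed values: "Missing values within a course of measurements on treatment will be interpolated".

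**The draws.** Footnote 22 of the protocol flow chart, attached to the safety laboratory row at Visits 10, 12 and 14, says: "Only blood sampling for haematology and urine dipstick test will be performed". FFA has its own row and is marked at every visit from 8 to 15.

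**The concern.** Protocol 7.5 and the SAP's own general safety rule would give lipid and FFA tables of observed values only. SAP 7.8.2 asks for imputed tables as well, and SAP 4 does not record the difference. That is an undeclared departure from the protocol.

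The sampling schedule makes it worse for lipids. SAP Table 6.7: 3 is one window table for FPG, vital signs and all safety laboratory data, with eight on-treatment windows. The SAP gives separate window tables to HbA1c, weight and waist (Table 6.7: 2) and to biomarkers and bone markers (Table 6.7: 4), which are drawn less often. Lipids have none. A programmer who applied Table 6.7: 3 and the LOCF rule literally would produce three lipid columns at visits where no lipid sample is planned, each with nearly full N.

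**Working it through.** **Plan's own figure.** Protocol 7.7 needs 50 completers over two doses, so 25 per arm, with about 20% dropout: 25 / (1 − 0.20) = 31.25, rounded up to 32 per arm, 64 in total. This reproduces the plan, so N = 64 and 20% dropout are used below.

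**Which windows contain a scheduled lipid draw.** Flow-chart day ± 7 against SAP Table 6.7: 3:

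| Visit | Draw, days | Window, days |
|---|---|---|
| 8 (Week 4) | 22–36 | 2–42 |
| 9 (Week 8) | 50–64 | 43–70 |
| 11 (Week 20) | 134–148 | 113–168 |
| 13 (Week 36) | 246–260 | 225–280 |
| 15 (Week 52) | 358–372 | from 337 |

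Each draw falls only in its own window. The windows for Week 12 (71–112), Week 28 (169–224) and Week 44 (281–336) contain none: 3 of 8 for lipids, 0 of 8 for FFA.

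**Make-up of those three columns under LOCF-IR.** Assumption, not in the documents: the 64 × 0.20 = 12.8 dropouts are spread evenly over 364 days. For a window from day a to day b:
- stopped before it = 12.8 × (a − 1) / 364 (carried forward)
- stopped inside it = 12.8 × (b − a + 1) / 364 (may have an observed end-of-treatment value)
- still on treatment after it = 64 minus both (interpolated, if a later on-treatment value exists)

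| Column | Before | Inside | After | After / 64 |
|---|---|---|---|---|
| Week 12 | 2.5 | 1.5 | 60.1 | 94% |
| Week 28 | 5.9 | 2.0 | 56.1 | 88% |
| Week 44 | 9.8 | 2.0 | 52.2 | 82% |

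Interpolated plus carried forward is 62.6, 62.0 and 62.0 of 64, about 97–98%. A patient who stops later without a further on-treatment sample moves from interpolated to carried forward; the total does not change.

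Only those who stop inside a window could contribute an observed value from a planned visit, and not all would. Flow-chart footnote 20 allows the end-of-treatment visit up to 7 days after the last dose, whereas SAP 7.8.2 counts laboratory values as on-treatment for 3 days only.

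**Week 52.** Stopped before day 337: 12.8 × 336 / 364 = 11.8; stopped at any time: 12.8. So about 12 to 13 of 64 values (18–20%) would be carried forward. With exactly 50 completers it is 64 − 50 = 14 (22%). At 10% dropout the range is 5.9 to 6.4; at 30%, 17.7 to 19.2.

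**Spread.** Weeks 28 and 44 lie midway between scheduled draws. With equal variances and between-visit correlation r, an average of two values has SD √((1 + r) / 2) times that of one value: 0.87 at r = 0.5 and 0.95 at r = 0.8. Interpolated values would show an SD about 5–13% too small. The correlations are assumed.

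**With OC-IR only.** Lipids have five populated visits (Weeks 4, 8, 20, 36, 52), with about 64 × 0.80 = 51 patients at Week 52. FFA keeps all eight.

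**The case against.** **The SAP knows what it wants for lipids.** The LOCF paragraph of 6.6, Table 6.3: 1 and 7.8.2 all name LOCF-IR, so a reader might infer a flat self-contradiction where there is a general rule with a specific exception. That stands for lipids within the SAP. It does not settle the conflict with protocol 7.5, which SAP 4 leaves unmentioned. Nor does it cover FFA: the 6.6 exception speaks of lipid parameters, and 7.8.2 lists FFA separately from them.

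**The SAP already accepts last values for safety laboratory data.** The safety sentence goes on: "Missing safety data will not be replaced, but an analysis of the changes from baseline to the last available value under treatment". For a dropout with an on-treatment value, LOCF-IR at Week 52 shows essentially that same number. This weakens the Week 52 point, although LOCF-IR labels the value Week 52 and substitutes baseline where no on-treatment value exists.

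**The three columns are conditional.** Weeks 12, 28 and 44 are in Table 6.7: 3 because FPG, vital signs and haematology need them. The SAP does not say that lipid tables will print them, or that an unscheduled measurement counts as missing. This stands. A reader might infer that three of eight columns will be wholly interpolated. The documents do not support that: it depends on two unstated choices, some values would be carried forward or observed at early end of treatment, and FFA is unaffected.

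**Nothing is hidden.** OC-IR tables appear beside the LOCF-IR ones, the lipid model uses OC-IR, and the trial has no confirmatory testing. This also stands, and it limits the severity.

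**Conclusion.** The conflict is real, and its consequences are small. The SAP plans imputed tables for safety laboratory parameters that the protocol says will not be imputed, and does not declare this.

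The figures of 94%, 88% and 82% interpolated at Weeks 12, 28 and 44 rest on 64 patients, 20% dropout spread evenly, use of all eight Table 6.7: 3 windows for lipids, and treating undrawn visits as missing. The Week 52 count of about 12 to 13 of 64 (about 6 to 19 at 10–30% dropout) needs only the dropout assumptions.

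A reader might infer that the trial's safety conclusions are at risk. They are not: the primary endpoint is drug-related adverse events, the secondary is HbA1c, and neither uses these tables. SAP 5.4 and 6.4 are not visible in the public text, so any further classification of lipids there could not be checked. Severity: minor.

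**What to change.** Delete LOCF-IR for lipids and FFA in SAP 6.6, SAP 7.8.2 and the matching entry of Table 6.3: 1. Keep the OC-IR tables and the OC-IR MMRM. Restrict lipid visit levels, in both tables and MMRM, to Weeks 4, 8, 20, 36 and 52. This second step is needed even without LOCF-IR: otherwise the OC-IR tables and the model could carry three nearly empty visit levels. FFA keeps its eight visits.

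If the sponsor prefers to keep LOCF-IR, SAP 4 should record it as a departure from protocol 7.5, the safety paragraph of SAP 6.6 should name the exception and say whether it includes FFA, and interpolation should be ruled out at visits with no scheduled draw.

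The cost is a few lines of SAP text and fewer tables to program. No data collection changes, and nothing is lost that the OC-IR tables and MMRM do not already provide.
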